1. STUDY OBJECTIVES

1.1 **Primary Study Aims:** Determine the feasibility of an integrated psychosocial treatment (ACT + MBRP) in veterans with chronic pain with evidence of opioid-related problems. Chronic pain patients ($n = 120$) who are receiving opioid therapy and who are identified as opioid misusing, abusing, or dependent will be recruited from the Albuquerque Veterans Administration (VA) Hospital. Participants will be randomized to receive standard care or standard care in addition to ACT+MBRP. **Hypothesis 1: Feasibility of recruitment:** Given the high prevalence of both chronic pain and opioid-related problems in VA populations, we hypothesize it will be possible to recruit our target sample size ($n = 120$) within a 15-18 month timeframe. **Hypothesis 2: Feasibility of retention:** Drop-out rates will be consistent with other trials of similar psychosocial interventions for chronic pain (i.e., < 20%^{5,21-23}).

1.2 **Secondary Study Aims:** To examine weekly progress on specific therapy targets (e.g., pain acceptance, self-compassion, opioid craving) in the interventions in order to identify potential mechanisms of change and to identify the choice of intermediate endpoints for a larger randomized clinical trial.

Hypothesis 1: Evidence of treatment mechanisms: The combined ACT+MBRP treatments will be associated with changes in treatment mechanisms specified within the therapeutic models and in a manner consistent with that of previous work on ACT and MBRP, in comparison with standard care.

Hypothesis 2: Selection of intermediate endpoints: Weekly progress measures will provide data indicating measures of treatment-specific mechanisms that are most sensitive to change. We hypothesize that acceptance of pain discomfort will be most sensitive to change in ACT and that reductions in reactivity to substance craving will be most sensitive to change in MBRP.

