5. STUDY INTERVENTIONS

5.1 Interventions, Administration, and Duration

Intervention Conditions—All participants will continue to receive standard care for chronic pain within the VA. In addition, one-half of participants will be randomized to also receive ACT plus MBRP.

Standard Care: All conditions will also receive standard treatment as usual, as indicated by treatment plan and not manipulated by the research team. Consistent with national and VA standards^{14,15}, care at the recruitment sites typically consists of noninvasive interventions, such as analgesic pain medications (e.g., opioids, NSAIDs, anti-epileptics), topical solutions (e.g., lidocaine), physical therapy, and massage, as well as limited invasive interventions (e.g., injections, radiofrequency denervation).

Acceptance and Commitment Therapy (Weeks 2–9): The ACT intervention is based on the standardized and manualized protocol of [name] and Sorrell¹⁶, which consists of weekly 90-minute group meetings over eight weeks. The protocol has been successfully used in previous clinical trials (e.g.,^{17,18}) and is currently available on the VA's Evidence-Based Practice Sharepoint website. Over the course of the group meetings, participants will identify areas of meaningful functioning that have been adversely impacted by pain, learn methods to enhance pain willingness in the service of these meaningful areas, and practice present-focused awareness skills. Group sessions will include discussions of the impact of pain and distress avoidance, identify alternative to this avoidance and establish plans for behavior change, demonstration and role-playing exercises, and homework assignments. Participants will be provided with a treatment manual to help guide and inform practice outside of group sessions. Table 1 provides an outline of session content for the eight week ACT intervention. We anticipate enrolling approximately eight patients per group.

Table 1: Overview of ACT Treatment Sessions

Session	Objectives and Content
1	
a. Treatment orientation and overview.b. Review treatment history and evaluate it in terms of how it has worked relative to patient's goals and expectations.

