9.1 General Design Issues

Preliminary Analyses: Data will be analyzed for missing cases to detect any bias across research groups that might result from differential attrition and/or response omission. For example, participant characteristics to include gender, minority status, age, drinking history, pain duration and intensity, educational achievement, and previous treatment experiences will be compared for those participants retained in the study versus those lost to attrition. Furthermore, the data will be examined for both missing cases and outlier scores on measures. Variable distributions will be checked for normality and if necessary, transformations will be performed to normalize the distributions. We will compare demographics and primary study measures at baseline between randomized treatment groups, using Analyses of Variance (ANOVA) for continuous variables (or Kruskal-Wallis if parametric assumptions are violated) and using chi-square tests for categorical variables. Subsequent analyses will adjust for significant baseline differences among the randomized groups at $\alpha = 0.05$.

Analyses to Test Primary Aim Hypotheses: The primary analyses for Aim 1 will be descriptive, including calculating the percent of individuals enrolled in the study versus those eligible and the percent of individuals who remain in the study. We will pay particular attention to issues of retention, as the treatment program will occur over 12 weeks and this length may impact treatment completion (previous programs of ACT alone, which have lasted eight weeks, have had drop-outs of < 20%^{17,21}). Therefore, we will define multiple levels of treatment retention, including partial treatment completion (% of individuals who do not complete all sessions), treatment dropout (% of individuals who dropout of treatment but continue to do assessments), research dropouts (% of individuals who remain in treatment, but do not complete research assessments), and treatment + research dropouts (% of individuals who do not complete treatment for research assessments). We will further break down the enrollment and retention calculations by examining enrollment/retention differences by treatment group, gender, age race/ethnicity, and initial severity using cross-classification tables.

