9.2 Sample Size and Randomization

Commented [KV4]: Blocking

Statistical Power for Secondary Aims: We estimated statistical power for the mediation analyses using parameter estimates from prior studies of mediation following ACT for chronic pain⁵ and following MBRP for substance use disorders^{7,63} to estimate the effect sizes for the behavioral measures in the current study. Following ACT, numerous behavioral measures significantly mediated changes in disability, depression, pain-related anxiety, medical visits, and number of classes of prescribed analgesics, with large mediation effect sizes. The prior studies of MBRP have found that experiential avoidance, awareness, and nonjudgment significantly mediated the association between treatment and changes in craving ($\alpha = 0.56$; $\beta = -0.43$) and that craving significantly mediated the association between treatment and changes in substance use ($\alpha = -0.20$; $\beta = 0.71$). Based on these effect sizes and power estimates for testing mediation derived from a simulation study⁷¹, we will have power greater than 0.80 to detect significant mediating effects with the proposed sample size of 120.

Examining mechanisms of change assumes that treatment influences change in the clinical outcome measures at follow-up, thus we also estimated the power to detect a main effect of treatment on the clinical outcome measures. Effect size estimates were drawn from prior studies of ACT for patients with chronic pain^{5,23,60,72} and MBRP for substance use disorders^{52,63,73}. The effect sizes for ACT in comparison to treatment as usual or active treatment for chronic pain have ranged from 0.29 to 1.09. The effect sizes for MBRP in comparison to treatment as usual for substance use and craving have ranged from 0.21 to 0.52. Based on these studies, we estimate a minimum average effect size of $d=0.25$. Using a mixed-effects linear model with $\alpha=0.05$ (two-tailed test), three repeated assessments (baseline, end of treatment, 6-month follow-up), and a correlation among repeated measures of 0.43 (based on prior studies) we will need 60 subjects per condition (total $n = 120$) for 80% power to detect a main effect of ACT+MBRP in comparison to standard care.

Treatment Assignment Procedures

We will use a random order variable-sized block randomization procedure with block sizes of 2, 4, and 6. The investigators will be blind to the size of each block and randomization allocation.

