9.5.1 Primary Outcome

The outcome for Aim 1 will be descriptive, including calculating the percent of individuals enrolled in the study versus those eligible and the percent of individuals who remain in the study. We will pay particular attention to issues of retention, as the treatment program will occur over 12 weeks and this length may impact treatment completion (previous programs of ACT alone, which have lasted eight weeks, have had drop-outs of < 20%^{17,21}. The assessment of this latter primary outcome will occur at each treatment meeting (as this is the only way to assess retention) and follow-up.

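### Primary Hypothesis 2 (drop-out below 20%) is to be read from a bare percentage with no interval, named denominator or stated precision; near 20% that reading is unreliable

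*Combined protocol and SAP*

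**What the plan says.** Section 1.1 lists feasibility of retention as Hypothesis 2 of the primary aim: "Drop-out rates will be consistent with other trials of similar psychosocial interventions for chronic pain", followed by a numerical limit of under 20%.

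The part of section 9.1 on testing the primary hypotheses states: "The primary analyses for Aim 1 will be descriptive". The retention statistic is "the percent of individuals who remain in the study". The same paragraph adds: "we will define multiple levels of treatment retention, including partial treatment completion", and goes on to list three further levels, which separate leaving treatment, leaving the assessments, and leaving both. Cross-classification by arm and participant characteristics is planned. Section 9.5.1 repeats the descriptive plan and adds no criterion.

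The power text in section 9.2 is headed "Statistical Power for Secondary Aims". It covers mediation and the treatment effect on clinical outcomes. The only 95% intervals planned in section 9 are bootstrap intervals for the mediated effect, which is also a secondary aim.

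**The concern.** The plan states a hypothesis with a number in it and then supplies only a percentage to judge it by. The one comparison available is whether the observed figure is under 20%. With 60 or even 120 people, sampling error is as large as the differences that matter around that limit, so one participant can move the reading from met to not met.

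Two things must also be settled before the comparison means anything. None of the four drop-out levels is tied to the 20%. The denominator could be the 60 assigned to ACT+MBRP or all 120.

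True rates near the limit are plausible on the plan's own account. Section 9.1 warns that 12 weeks may affect completion, whereas the ACT-only precedents under 20% ran for eight. Section 2.1 says that opioid-dependent patients are at risk of not completing. What is at stake is the stated conclusion on one of the two primary hypotheses of a trial meant to prepare a larger one.

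**Working it through.** **Inputs.** Limit: 20% (section 1.1). Number treated: section 5.1 says "one-half of participants will be randomized to also receive ACT plus MBRP", so 120 / 2 = 60. Number in all: 120. The true drop-out rate is unknown, so a range of 10% to 30% is shown (assumption).

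**The plan's own figure.** There is none for retention. The 60 per condition in section 9.2 belongs to a secondary aim. It reproduces as a group-by-time interaction with f = 0.25/2 = 0.125, three assessments and correlation 0.43: noncentrality 0.125² × 120 × 3 / (1 − 0.43) = 9.87 on 2 and 236 degrees of freedom, giving power 0.805. It says nothing about retention.

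**Step 1: the bare comparison.** An observed rate below 20% means at most 11 of 60 (12/60 = 20.0%) or at most 23 of 120 (24/120 = 20.0%). With X ~ Binomial(n, p), the chance of a misleading reading is P(X ≤ 11) or P(X ≤ 23) when p is 20% or more, and the complement when p is below 20%.

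| True drop-out | Misleading reading | n = 60 | n = 120 |
|---|---|---|---|
| 10% | observed 20% or more | 1.5% | 0.1% |
| 15% | observed 20% or more | 18% | 8% |
| 18% | observed 20% or more | 39% | 32% |
| 22% | observed below 20% | 31% | 27% |
| 25% | observed below 20% | 15% | 8% |
| 30% | observed below 20% | 3% | 0.5% |

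**Step 2: what one participant does.** The exact (Clopper-Pearson) two-sided 95% limits for x of n are the 2.5% quantile of Beta(x, n − x + 1) and the 97.5% quantile of Beta(x + 1, n − x).

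- 11/60 = 18.3%: 9.5% to 30.4%
- 12/60 = 20.0%: 10.8% to 32.3%

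The intervals nearly coincide, yet the bare comparison gives opposite answers.

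**Step 3: where the two-sided 95% interval clears 20%.**

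| Drop-outs | Exact 95% interval | Position relative to 20% |
|---|---|---|
| 5/60 (8.3%) | 2.8% to 18.4% | wholly below |
| 6/60 (10.0%) | 3.8% to 20.5% | includes 20% |
| 18/60 (30.0%) | 18.8% to 43.2% | includes 20% |
| 19/60 (31.7%) | 20.3% to 45.0% | wholly above |
| 15/120 (12.5%) | 7.2% to 19.8% | wholly below |
| 16/120 (13.3%) | 7.8% to 20.7% | includes 20% |
| 33/120 (27.5%) | 19.7% to 36.4% | includes 20% |
| 34/120 (28.3%) | 20.5% to 37.3% | wholly above |

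**Step 4: precision.** At 20%, the approximate half-width is 1.96 × √(0.2 × 0.8 / n). This is 0.101 for n = 60 and 0.072 for n = 120, so about ±10 and ±7 points.

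All of these figures treat drop-outs as independent. Section 5.2 allows therapy groups of four to ten, and correlated drop-out within groups would widen the intervals in the treated arm.

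**The case against.** Descriptive analysis is normal in a feasibility trial. The hypothesis is that drop-out will resemble that of other trials, with 20% as a literature benchmark; nothing requires the trial to demonstrate a rate below 20% with 95% confidence. Four retention levels broken down by subgroup are not a single pass-or-fail number. The phrase about individuals remaining in the study reads most naturally as all 120, where the error rates are lower. Misreading a true 18% as 20% has little practical consequence. Under an interval rule most trials with true rates near 20% would be inconclusive: at n = 60, about 90% at a true 15%, 97% at 20% and 85% at 25%.

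Much of this stands. A descriptive primary analysis is acceptable, and no powered test or larger sample is called for. Section 1.1 also frames recruitment as reaching 120 within 15 to 18 months, a target that is hit or missed; only the enrolment percentage in 9.1 needs an interval.

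What does not stand is leaving the interval out. The section is presented as testing the primary hypotheses and the hypothesis carries a number, so some comparison with 20% will be made. Pooling all 120 reduces the problem but does not remove it: 27% at a true 22% and 32% at a true 18%. A frequent inconclusive reading is what the data can support.

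A reader might infer that the trial has a go/no-go rule at 20%. The documents set none and do not tie the next trial to that figure.

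**Conclusion.** The point holds as a gap in reporting and interpretation. The plan gives the retention hypothesis a numerical limit but no interval, drop-out level, denominator or stated precision. For true rates of roughly 15% to 25%, the bare comparison misleads in about 15% to 40% of trials with 60 treated at the rates tabulated (8% to 32% with 120).

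Two stronger readings go too far. One is that the verdict would often be wrong whatever the true rate: at n = 60 the error is 1.5% at a true 10% and 3% at 30%. The other is that a rate under 20% could be shown with an observed drop-out of up to 10%. That cut-off (6/60) comes from a one-sided 95% bound, which the plan does not specify; the two-sided 95% interval for 6/60 reaches 20.5%, so the two-sided cut-off is 5/60. Nor do the documents settle that 60 is the denominator.

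The figures rest on exact binomial calculation, full enrolment of 120 with equal arms, and independent drop-out.

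**What to change.** - **Sections 9.1 and 9.5.1.** Report the Aim 1 enrolment and retention percentages with exact (Clopper-Pearson) 95% confidence intervals.
- **Same sections.** Name the drop-out level and the denominator compared with 20%, for example treatment drop-out among the 60 assigned to ACT+MBRP.
- **Same sections.** Describe Hypothesis 2 as supported only when the two-sided 95% interval lies wholly below 20% (at most 5/60, or at most 15/120 if all participants are used). Describe it as contradicted only when the interval lies wholly above (at least 19/60, or at least 34/120). Otherwise give the estimate and interval as compatible with rates on both sides of 20%. If enrolment differs from plan, recompute the cut-offs from the actual denominator.
- **Section 9.2.** State that 60 gives about ±10 points at 20% and 120 about ±7, before any allowance for clustering of drop-out within therapy groups.

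The cost is a few sentences. The analysis stays descriptive, with no added enrolment or data collection. The downside is a less favourable likely conclusion: 6 to 18 drop-outs of 60 (16 to 33 of 120) would be reported as inconclusive.

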4.3 Study Enrollment Procedures

A brief screening questionnaire that inquires about eligibility criteria will be administered via telephone to patients receiving opioid therapy as part of their treatment for chronic pain at the VA who are interested in participating in the research study. Interested individuals who meet initial screening criteria will be seen at the VA for an in-person screening where the procedures and voluntary nature of the study will be fully explained. Participants will meet with a trained Research Assistant (RA) in a private assessment office at the VA for the opioid use and psychiatric screening and to obtain Human Research Protections Office (HRPO) approved informed consent. The in-person screening will consist of self-reported opioid misuse behaviors on the COMM, as well as a structured clinical interview using the Substance Use Disorders model of the SCID, which will enquire about opioid use patterns.

Anticipated wait time from screening to baseline assessment and randomization. After the initial screening, eligible participants will be scheduled for an in person assessment to complete informed consent and baseline assessments. This assessment will occur within 14 days (and ideally within 7 days) of screening. Immediately following completion of informed consent and assessment, participants will be randomized to treatment condition.

Anticipated wait time from randomization to intervention beginning. We plan to begin at least one new group per month, therefore, wait time for most participants is anticipated to be less than one month from the time of study enrollment. As noted, we have planned for recruitment of eight individuals per month, which corresponds to our target group size. Should recruitment be faster than expected, we can accommodate up to ten individuals in each group to keep waiting times to a minimum. Furthermore, by the third month of providing intervention, we will be running three treatment groups at any one point in time (as each group will receive treatment for three months total). If the participant backlog surpasses six individuals (which is sufficient to compose a group for treatment), we will be able to add a fourth treatment group.

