5.2 Handling of Study Interventions

Interventions will be delivered in a group format. The target number of participants for each group will be up to eight individuals, although it is possible to conduct the group with as few as four participants or as many as ten. Both interventions will be manualized as described in section 5.1 above. Due to the nature of the intervention, blinding to condition will not be possible.

Number of therapists: There will be a minimum of two study therapists for each group (one the RA paid on the grant and the other a volunteer RA). Study therapists will be appointed through the University of New Mexico's (UNM) graduate program in clinical psychology. The volunteer RA will receive practicum credit through UNM in lieu of payment. All therapists will be advanced post-Masters degree doctoral students (i.e. with necessary approval of the UNM's Clinical Committee to engage in clinical work) who will have received four and one half days of training (32.5 hours total) in ACT (provided by [name]; training completed January 2015) and MBRP (provided by [name]; training completed December 2014). Prior to leading any treatment sessions, therapists will be required to demonstrate a minimum level of competency, as outline by ACT and MBRP training guidelines. Instructors will also receive weekly supervision from an outside supervisor with specific expertise in ACT and MBRP.

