6.2.5.1 Participant Compensation

Remuneration for each of the assessments is as follows: Participants will receive \$60 for completion of the baseline session, \$5 per week for completing weekly assessments during active treatment (\$60 total), \$50 for completing the end of treatment assessment (week 13), and \$50 for completing the six-month follow-up (week 37), totaling \$220. Individuals who complete all assessments will be given a \$50 bonus at the 6-month follow-up, for a maximum compensation of \$270.

Participant costs per year are as follows:

Year 1: \$9,680	(64 baseline, 64 X \$60=\$3840; 64 weekly treatment, 64 X \$60=\$3840; 40 post-treatment; 40 X \$50=\$2000).
Year 2: \$19,520	(56 baseline, 56 X \$60=\$3360; 56 weekly treatment, 56 x \$60= \$3360; 80 post-treatment, 80 X \$50=\$4000; 88 six month follow-up, 88 X \$50=\$4400; 88 bonus six month maximum completion, 88 X \$50=\$4400).
Year 3: \$3,200	(32 six month follow-up, 32 X \$50=\$1600; 32 bonus six month maximum completion, 32 X \$50=\$1600).

The participant compensation record is displayed in Appendix VI.

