Analyses to Test Secondary Aim Hypotheses. The primary goal of Aim 2 is to identify potential mechanisms of change and intermediate endpoints for future randomized clinical trials comparing ACT+MBRP to standard care. We will accomplish this goal by examining initial level and changes in targeted mechanisms over time during the course of treatment, as well as the association between changes in targeted mechanisms during treatment and 6-month follow-up measures of clinical outcomes. Targeted mechanisms will include (1) pain acceptance (2) psychological flexibility, (3) experiential avoidance, (4) opioid craving, and (5) reactivity to pain and craving, and will be examined using latent growth curve models with fixed effects of treatment and random effects of time. These analyses will provide an estimate of the initial level of each targeted mechanism (i.e., intercept) and the change in the targeted mechanisms over time (slope). Clinical outcome measures will include pain interference, pain behavior, and opioid misuse and will be examined using mediation analyses within the context of latent growth curve modeling⁶⁴, as we have done in prior studies^{63,65}. Specifically, as shown in simplified form in Figure 2, we will examine whether initial level (intercept) or changes (slope) in the targeted mechanisms ("M" in figure 2) during treatment mediate the effect of treatment on 6-month clinical outcomes, controlling for baseline levels of the outcomes. These analyses will also provide a test of Aim 2 Hypothesis 2, which is to identify those measures that are most sensitive to change (measures with the largest slope). Identifying measures that are more sensitive to change will help us in identifying intermediate endpoints for a larger RCT. Validation of intermediate endpoints is challenging and it is often recommended that meta-analytic methods be used⁶⁶, but alternative methods have been developed that allow for the evaluation of endpoints in mental-health clinical trials⁶⁷.

Figure 2. Simplified mediation model (excludes residual terms and covariances)

models will be estimated using the product of coefficients method⁶⁸, which provides an estimate of the mediated effect by multiplying regression coefficients for the regression of the mediators (e.g., slope of targeted mechanism) on treatment condition (i.e., a-path or α) and for the regression of the clinical

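### The Aim 2 growth and mediation models ignore therapy groups, so treatment-effect and a-path standard errors are too small if outcomes correlate within groups (modestly for groups of four)

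*Combined protocol and SAP*

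**What the plan says.** - **Delivery.** Section 5.2: "Interventions will be delivered in a group format", and "There will be a minimum of two study therapists for each group". Section 5.1 expects about eight patients per group; 5.2 sets a target of up to eight and a workable range of four to ten. Standard care follows each person's own treatment plan, with no study groups.
- **Allocation and pace.** Section 5.1: "one-half of participants will be randomized to also receive ACT plus MBRP". Section 4.3: "We plan to begin at least one new group per month", and "we have planned for recruitment of eight individuals per month, which corresponds to our target group size". Section 1.1 aims to recruit 120 "within a 15-18 month timeframe".
- **Analysis.** Section 9.1 states that the mechanisms "will be examined using latent growth curve models with fixed effects of treatment and random effects of time". Mediation uses the product of coefficients, with the mechanism slope regressed on treatment as the a-path. Estimation is by maximum likelihood, with a 95% bootstrap interval whose resampling unit is not stated.
- **Power.** Section 9.2 derives 60 per arm with no allowance for therapy groups.
- **Data capture.** The case report form in Appendix III records the assigned arm only. None of the forms shown has a therapy-group field.

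**The concern.** This is a partially nested design. Twelve weekly sessions with the same group members and therapists can make outcomes in the ACT+MBRP arm correlate within a group, while standard-care participants remain independent. A model containing only treatment and time effects attributes all between-person variation to individuals, so the variance of the ACT+MBRP mean is underestimated when the correlation is positive. Resampling individual participants in the bootstrap reproduces the same error.

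The stake is the inferential part of Aim 2: the comparison of mechanism change with standard care, the mediation intervals, and the treatment effect on clinical outcomes that mediation presupposes. These results are meant to guide the choice of intermediate endpoints for a larger trial.

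**Working it through.** **The plan's own figure.** Section 9.2 gives d = 0.25, correlation 0.43, three assessments, two-sided alpha 0.05, 60 per arm and 80% power. It reproduces as a group-by-time F test with f = d/2 = 0.125:

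noncentrality = 120 × 0.125² × 3 / (1 − 0.43) = 9.87, df 2 and 236, power 0.805.

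All 120 participants are taken as independent. (A between-arm main effect averaged over the three assessments would give power of only 0.41 at 60 per arm. That is a separate matter, and for this reason the power figures under the fix show relative loss only.)

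**Group size.** Section 6.2.5.1 budgets 64 + 56 = 120 baselines. At eight a month this is 120/8 = 15 months, inside the 15–18 month window. Half go to therapy, so about four a month enter at least one new monthly group: 60/4 = 15 groups of four. Filling groups to the stated target of eight gives 60/8 = 7.5, or about 8 groups. I carry both.

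**SE of the arm difference.** The design effect applies to one arm only:

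DE = 1 + (m − 1) × ICC; true/naive SE = √((1 + DE)/2); understatement = 1 − 1/ratio.

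Example, m = 4 and ICC = 0.05: DE = 1.15, ratio = √1.075 = 1.037, understatement 3.6%.

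| Group size | ICC | SE ratio | SE understated | Type I error, simple arm difference | Type I error, ML slope contrast (z test) |
|---|---|---|---|---|---|
| 4 | 0.01 | 1.007 | 0.7% | 5.2% | 5.7% |
| 4 | 0.05 | 1.037 | 3.6% | 5.9% | 6.3% |
| 4 | 0.10 | 1.072 | 6.7% | 6.8% | 7.3% |
| 8 | 0.01 | 1.017 | 1.7% | 5.4% | 5.8% |
| 8 | 0.05 | 1.084 | 7.7% | 7.0% | 7.6% |
| 8 | 0.10 | 1.162 | 13.9% | 9.0% | 9.6% |

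Type I errors are from 200,000 simulated trials per cell: 60 controls against 15 groups of four, or 7 groups of eight plus one of four. The slope contrast assumes complete weekly data, and its ICC is that of the estimated slope. Its z test already runs at 5.5% without clustering, so only the excess over 5.5% belongs to this point.

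**Mediated effect.** I set a = 0 and b = 0.71 (a b-path in 9.2, taken as standardised), with the same ICC on mediator and outcome residual and the slope treated as observed. The participant-level bootstrap used 500 resamples. Simulation error is about 0.1 point.

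| ICC | Interval excludes zero, groups of 4 | Groups of 8 |
|---|---|---|
| 0 | 5.8% | 5.7% |
| 0.01 | 5.7% | 6.1% |
| 0.05 | 6.7% | 8.0% |
| 0.10 | 7.6% | 9.7% |

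Against about 5.8% with no clustering, the excess at ICC 0.05 and 0.10 is about 0.9 and 1.8 points (four), or 2.2 and 3.9 points (eight). At 0.01 it is negligible. A separate simulation at ICC 0, 0.05 and 0.10 gave 5.9%, 6.9% and 7.3% (four) and 5.9%, 8.1% and 9.6% (eight), with similar inflation at b = 0.43, the other b-path size in 9.2.

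The full latent growth mediation model with missing data was not simulated.

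**The case against.** **The effect is small and the aim exploratory.** With groups of four, clustering adds one or two points of error at most over the assumed ICCs. The primary aim is descriptive, and ranking measures by slope is essentially unaffected. All of this stands, and it limits the weight of the point. But Aim 2 does plan a comparison with standard care, 95% intervals and a stated power for mediation, so the standard errors matter there.

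**Four per group is an inference.** Section 5.1 expects about eight, and an average of four sits at the floor in 5.2, so some groups might wait or merge. That is fair: the monthly schedule and the stated group size do not fit together easily. Both sizes are therefore shown, and the larger one makes the problem worse.

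**Mediation inflation depends on the b-path.** At b = 0.2, with groups of four, the bootstrap interval excludes zero in only 2.9%, 3.4% and 3.8% of trials at ICC 0, 0.05 and 0.10, below nominal throughout. This is correct for a weak b-path, but the b-paths in 9.2 are 0.43 and 0.71 in size, and at those values the inflation appears.

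**Group membership could be rebuilt.** The payment log in Appendix VI has a dated line for each treatment week, and attendance is tracked. With monthly starts this might identify most groups. It is a partial fallback and does not replace a group field.

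**Conclusion.** The concern holds. The plan treats participants as independent although one arm is treated in groups, and any positive within-group correlation makes the treatment-effect and a-path standard errors too small. The size is modest for groups of four (SE understated by 3.6% at ICC 0.05 and 6.7% at 0.10) and roughly double for groups of eight (7.7% and 13.9%); at ICC 0.01 it is negligible. These figures rest on assumed ICCs, equal-variance arms, near-constant group sizes and, for mediation, a b-path of the size in 9.2. Only the secondary aim is touched. The correction should be made because it is cheap, and because it may not be possible afterwards if group ID is not recorded.

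**What to change.** - **Record** therapy-group ID when a participant joins a group, for example on the attendance record kept under section 5.4.
- **Model.** For treatment effects and the a-path, include a group random effect in the ACT+MBRP arm only, placed on the slope or post-baseline outcome and not on the intercept, which precedes the group. Alternatively, use group-clustered SEs. Either way use Satterthwaite-type degrees of freedom, and fall back on the clustered SE if the group variance cannot be estimated. In simulation, the clustered variance with these degrees of freedom held type I error at 5.0% (four) and 5.1–5.2% (eight).
- **Mediation.** Build intervals from the group-adjusted a-path SE with Monte Carlo or distribution-of-product limits. In simulation, Monte Carlo limits excluded zero in 4.7–5.5% of trials with a = 0.
- **Power.** State in 9.2 that the 80% assumes no group clustering.
- **ICC.** Report any estimate only with its interval, and do not plan the larger trial on the point estimate alone. An estimate of 0.05 would carry a 95% interval of about −0.12 to 0.36 (15 groups of four) or −0.06 to 0.39 (8 groups of eight).

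The administrative cost is SAP wording and one data field. The statistical cost exists even without clustering. If the unadjusted test had 80% power at ICC 0:

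| ICC | Adjusted power, groups of 4 | Adjusted power, groups of 8 | Mediation interval wider by (4 / 8) |
|---|---|---|---|
| 0 | 0.78–0.79 | 0.77 | 4% / 5% |
| 0.05 | 0.75–0.76 | 0.69–0.70 | 8% / 15% |
| 0.10 | 0.72–0.73 | 0.63–0.64 | 12% / 24% |

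The power ranges reflect two ways of setting the effect that gives 80% (0.5157 or 0.5116 SD).
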